## LIST OF ABBREVIATIONS

AE	adverse event
AUC0-∞	Area under the concentration versus time curve from time = 0 to infinity.
AUC0-12	Area under the concentration versus time curve from time = 0 to t = 12 hours.
BUN	blood urea nitrogen
CFR	Code of Federal Regulations
Cmax	maximum concentration
CRF	case report form
CRP	C-reactive protein
ESR	erythrocyte sedimentation rate
FDA	Food and Drug Administration
GCP	Good Clinical Practice
HIPAA	Health Insurance Portability and Accountability Act of 1996
ICF	informed consent form
ICH	International Conference on Harmonisation
IEC	Independent Ethics Committee
IRB	Institutional Review Board
IV	intravenous
PI	Principal Investigator
PK	pharmacokinetic
SAE	serious adverse experience
Tmax	time to C max

## PROTOCOL SYNOPSIS

TITLE	The Effects of Single Dose Rifampin on Pharmacokinetics of Fluvastatin in Healthy Volunteers
NUMBER OF SITES	1
RATIONALE	The effect of OATP1B1 transporter inhibition at clinical doses of fluvastatin, a BDDCS class 1 drug, has not been studied to date. A single dose of IV rifampin can be used as model OATP1b1 inhibitor to evaluate the significance of OATP1B1 transporter effects on fluvastatin disposition.
STUDY DESIGN	This is two-period, randomized, unblinded, crossover clinical trial.
PRIMARY OBJECTIVE	The primary objective is to determine whether or not inhibition of OATP1B1-mediated drug transport of fluvastatin will be clinically significant.
NUMBER OF SUBJECTS	10-12
SUBJECT SELECTION CRITERIA	
Inclusion Criteria:
 
 
• Healthy male or female, ages 18-65 years old, with no current medical conditions or active diagnoses as determined by the study doctor based on history, physical exam, and laboratory evaluations.
 
• Subjects who take no other medications two weeks prior to the study and during the time course of the study including prescription medications, over-the-counter medications, dietary supplements, or drugs of abuse.
 
• Subjects able to maintain adequate birth control during the study independent of hormonal contraceptive use (use of condoms).
 
• Subjects able to abstain from grapefruit, grapefruit juice, oranges, orange juice, caffeinated beverages and/or alcoholic beverages from 7am the day before the study to completion of that study day.
 
• Participants determined to have normal liver and kidney function as measured at baseline (ALT: <math>\leq 2x</math> upper level of
 

	
normal (ULN), AST: <math>\leq</math> 2x ULN, SCr: <math>\leq</math> 1.5x ULN, T. Bili: 0.1-1.2mg/dL, Albumin: 3.4 – 4.7 mg/dL).
 
 
• BMI between 18.0 - 30 kg/m^2 o Subjects capable of fasting from food and beverages at least 8 hours prior to medication dosing.
 
• Be able to read, speak, and understand English.
 
• Subjects capable of providing informed consent and completing the requirements of the study.
 
 
Exclusion Criteria:
 
 
• Subjects with active medical problems
 
• Subjects on chronic prescription or OTC medication that cannot be stopped 2 weeks prior to and during the study.
 
• Subjects incapable of multiple blood draws (HCT < 30mg/dL)
 
• Subjects with a history of rhabdomyolysis
 
• Subjects with a history of drug-related myalgias
 
• Subjects with a history or diagnosis of hemorrhagic tendencies or blood dyscrasias
 
• Subjects with a history of GI bleed or peptic ulcer disease
 
• Subjects who smoke tobacco or have ongoing alcohol or illegal drug use
 
• Subjects who are pregnant, lactating, or trying to conceive during the study period
 
• Subjects allergic to fluvastatin or rifampin or any known component of the medications
 
• Anyone who in the opinion of the study investigators is unable to do the study
 

TEST PRODUCT, DOSE, AND ROUTE OF ADMINISTRATION	fluvastatin 20 mg by mouth as a 20 mg Lescol® capsule Rifampin 600mg IV infusion over 30 minutes (t = -30 minutes)
CONTROL PRODUCT, DOSE AND ROUTE OF ADMINISTRATION	fluvastatin 20 mg by mouth as a 20 mg Lescol® capsule

DURATION OF SUBJECT PARTICIPATION AND DURATION OF STUDY	subject will be on study for up to 2 days Screening: One 2-hour screening visit one week prior to the study Treatment: 13 hours stays in the CRC(separated by at least 1 day) The total time required is 27 hours over about 2 day period.
CONCOMITANT MEDICATIONS	Allowed: No concomitant medication allowed  Prohibited: subject will not allow to take any other medications two weeks prior to the study and during the time course of the study including prescription medications, over-the-counter medications, dietary supplements, or drugs of abuse.
PRIMARY ENDPOINT	The primary outcome will be fluvastatin AUC0-12h and AUC0- $\infty$ (AUC = area under the plasma concentration versus time curve).
SECONDARY ENDPOINTS	Secondary outcomes will include fluvastatin maximum plasma concentration (Cmax) and time to Cmax (Tmax) .
SAFETY EVALUATIONS	Safety evaluation will be determined by the incidence of adverse events. Subjects will be monitored on an ongoing basis while involved with the study by study personnel. Subjects will be screened with a medical history and physical examination by the study physician and have screening hematology, chemistries, liver, renal and coagulation laboratories. Subjects must have normal function of all major organs. At study completion, subjects will have repeat physical examination and repeat hematology, chemistries, liver, renal and coagulation laboratories for safety monitoring.
PLANNED INTERIM ANALYSES	Serious adverse events will be monitored by the committee on an ongoing basis throughout the study.
STATISTICS Primary Analysis Plan	AUC0- $\infty$ will be calculated using the trapezoidal rule from time 0 to Clast + Clast/ke. Parameters such as maximum plasma concentration (Cmax) and time to Cmax (Tmax) will be determined from the observed data. The terminal elimination rate constant (ke) will be obtained using linear regression of log transformed concentrations over the terminal log-linear decline phase. Oral clearance (CL/F) will be calculated using Dose/AUC0- $\infty$ . Other estimated pharmacokinetic parameters will be calculated using non-compartmental methods with

	WinNonlin Professional software (Pharsight, Inc., Mountain View, CA). Log-transformed pharmacokinetic parameters will be compared across treatments with analysis of variance for repeated measures. Differences will be regarded as statistically significant if $p < 0.05$ . Data will be presented as mean values with standard deviations. Each subject will serve as his/her own control. Differences in pharmacokinetic parameters between treatments will be calculated using student's paired t-test. Statistical calculations will be done using STATA 10.0 (StataCorporation, College Station, TX).
Rationale for Number of Subjects	Using a paired t-test and prior data, a sample size of $n=10$ in each group is needed to detect a 50% difference in $AUC_{0-12}$ between the two study regimens with a statistical power of 80% (two sided alpha = 0.05) and standard deviation of 50%. Due to the lesser effects of rifampin on fluvastatin AUC, the within subject variability can affect the sample size. We plan to enroll sample size of 12 subjects to maintain an adequate sample size in case of potential attrition.

## 1 BACKGROUND

Membrane transporters located throughout the body play an important role in drug absorption, disposition, metabolism, and elimination. The inhibition of many of these transporters has been linked to significant drug-drug interactions. Located on the sinusoidal membrane of hepatocytes, the Organic Anion Transporter Polypeptide transporter OATP1B1 is responsible for the uptake of substrates from the blood into the liver where they can be metabolized and cleared. When OATP1B1-mediated transport is inhibited with known inhibitors such as ritonavir, rifampin, or cyclosporine, drug metabolism and elimination into bile are diminished, resulting in elevated concentrations of the drug in the blood. Another important membrane transporter, Breast Cancer Resistance Protein or BCRP, present in the intestinal epithelia and liver, is also important for drug elimination. If BCRP is inhibited, drug concentrations in the liver and blood may also rise.

Statins are commonly prescribed cholesterol-lowering agents whose efficacy and safety is closely linked with the function of the BCRP and OATP1B1 transporters. These drugs must enter the liver to exert their efficacy. Compared to other statins like rosuvastatin and pravastatin, fluvastatin is extensively metabolized. It has a more hydrophobic profile making it highly permeable through the membranes and in theory less dependent on OATP1B1-mediated transport.

To predict hepatic uptake transporter effects on drug disposition, Wu and Benet developed the Biopharmaceutics Drug Disposition Classification System (BDDCS) system which categorizes drugs based on extent of metabolism and solubility characteristics. According to this classification system, the plasma exposure of Fluvastatin, a BDDCS class I drug should be minimally influenced by transporter effects.

### 1.1 Overview of Non-Clinical Studies

Available in vitro data demonstrates that inhibition of OATP1B1 by rifampin results in reduced rosuvastatin uptake in Human Embryonic Kidney (HEK293) cells, which implies the drug's significant dependence on the membrane transporter. Animal studies have also confirmed that rifampin significantly alters hepatobiliary transport of rosuvastatin and increases its plasma exposure (AUC) and Cmax.

### 1.2 Overview of Clinical Studies

Contrary to our expectations, one clinical study has demonstrated that co-administration of single-dose rifampin with 2 mg of fluvastatin results in significant increase in exposure of the cholesterol-lowering agent. However this study was conducted with one tenth to one

fortieth of the common dose of fluvastatin, and we believe that the effect of rifampin on fluvastatin exposure in this study to be due to the low concentration of fluvastatin.

Clinical studies have demonstrated that co-administration of single-dose rifampin with the BDDCS Class II drug atorvastatin results in marked increases in concentrations of the cholesterol-lowering agent. Similar studies with the BDDCS class III drug rosuvastatin and class II drug glyburide showed similar transporter effects which increased plasma concentrations of the two drugs when co-administered with a single dose of rifampin. These studies have demonstrated the significant effects of hepatic uptake transporters on the pharmacokinetics of BDDCS class II and III drugs. It is expected that these transporter effects will not be significant for BDDCS class I drugs like fluvastatin.

## 2 STUDY RATIONALE

Characterizing the effect of inhibition of hepatic uptake transporters by rifampin, on the pharmacokinetics of fluvastatin will advance our understanding of statin clinical pharmacology. It will give us a better understanding of the effects of hepatic uptake transporters on statin pharmacokinetics, statin drug-drug interaction and will serve as a validation check for the BDDCS classification system.

### 2.1 Risk / Benefit Assessment

There is minimum risk involved in this study. Only approved dosage of FDA approved medications are being used in this study. As outlined by the Data and Safety Management Plan for the study all precautions are being considered to uphold the safety and best interest of all participants. The subject may stop the study at any time for any reason.

There is no direct benefit for subjects to participate in the study.

## 3 STUDY OBJECTIVES

### 3.1 Primary Objective

The primary objective is to determine whether or not inhibition of OATP1B1-mediated drug transport of fluvastatin will be clinically significant. The study will assess if a IV dose of rifampin (to inhibit hepatic uptake transporters) immediately prior to oral fluvastatin dosing will have any effect on fluvastatin total drug exposure.

## 4 STUDY DESIGN

### 4.1 Study Overview

The effect of rifampin on the pharmacokinetics of fluvastatin will be studied in healthy volunteers in a two-period, randomized, unblinded, crossover clinical trial. On period 1 of the study, subjects will be randomized to one of two treatment groups:

- (i) one oral dose of fluvastatin (Lescol®) 20mg capsule
- (ii) one oral dose of fluvastatin (Lescol®) 20mg capsule immediately following a 30-min intravenous infusion of rifampin 600mg in 10ml Normal Saline.

The two study periods will preferentially be on a Tuesday and Thursday, separated by one day of washout. Subjects will be instructed to fast overnight the day before study periods 1 and 2, and for 3h post-dosing. In both treatments, venous blood samples (~8ml each) will be drawn at 0, 0.33, 0.67, 1, 1.5, 2, 2.5, 3, 4, 6, 9, 12h after fluvastatin dosing. Period 2 will begin after at least a 1-day washout when subjects will receive the second treatment, followed by blood draws at the same time points as after fluvastatin dosing alone.

	Period 1	Period 2
Group 1	A	B
Group 2	B	A

A= fluvastatin; B =rifampin +fluvastatin

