## **9.3 Pharmacokinetic Measurements**

Blood for determination of serum concentrations of fluvastatin will be collected 0, 0.33, 0.67, 1, 1.5, 2, 2.5, 3, 4, 6, 9, and 12h after fluvastatin dosing. Plasma will be separated and stored at -80°C until analysis of drug levels.

Plasma concentrations of fluvastatin and rifampin in all collected plasma samples will be measured via a previously validated tandem liquid chromatography mass spectrometry (LC-MS/MS) method. Determined plasma concentrations of fluvastatin will then be modeled using pharmacokinetic modeling software to calculate the corresponding AUC, oral clearance, and oral volume of distribution of fluvastatin in the treatment groups.

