### **10.3 Study Period 2 (Thursday of the week )**

- 1) Admit to Clinical Research Center (CRC) at UCSF** - During each study period, subjects will be admitted to the Clinical Research Center (CRC) at UCSF (12th Floor Moffitt Hospital). Subjects will be discharged after the 12 hour blood sample.
- 2) Urine Pregnancy Test** - For female subjects, a urine pregnancy test will be performed.
- 3) Catheter placement-** For the purpose of administering rifampin and drawing blood samples, two indwelling peripheral venous catheter will be inserted aseptically into the forearm vein by a nurse in the CRC immediately prior to medication administration. The rifampin catheter will be removed immediately after rifampin administration, the second catheter will be removed after the final blood draw. If the catheter malfunctions and needs to be removed prior to the last blood draw, a subject may choose to have remaining blood draws via peripheral venous needle sticks or have a new catheter placed.
- 4) Dose study medications:** Subjects will receive one of the following dose of medications:
  - a. Dose fluvastatin 20 mg by mouth as a 20 mg Lescol® capsule (t = 0)
  - b. Dose rifampin 600mg IV infusion over 30 minutes (t = -30 minutes) followed by a dose of fluvastatin 20 mg by mouth as a 20 mg Lescol® capsule (t = 0)The order in which subjects receive the above treatments will be randomized via random number generator.
- 5) Serial blood sampling-** Venous blood samples (8 mL) will be drawn at 0, 0.33, 0.67, 1, 1.5, 2, 2.5, 3, 4, 6, 9 and 12h after fluvastatin dosing. Plasma will be separated and stored at -80°C until analysis of drug levels.

**6) Safety Monitoring-** At study completion, subjects will have repeat physical examination and repeat hematology, chemistries, liver, renal and coagulation laboratories for safety monitoring.

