	
beverages from 7am the day before the study to completion of that study day.
 
 
• Participants determined to have normal liver and kidney function as measured at baseline (ALT: <math>\leq 2x</math> upper level of normal (ULN), AST: <math>\leq 2x</math> ULN, SCr: <math>\leq 1.5x</math> ULN, T. Bili: 0.1-1.2mg/dL, Albumin: 3.4 – 4.7 mg/dL).
 
• BMI between 18.0 - 30 kg/m^2 o Subjects capable of fasting from food and beverages at least 8 hours prior to medication dosing.
 
• Be able to read, speak, and understand English.
 
• Subjects capable of providing informed consent and completing the requirements of the study.
 
 
Exclusion Criteria:
 
 
• Subjects with active medical problems
 
• Subjects on chronic prescription or OTC medication that cannot be stopped 2 weeks prior to and during the study.
 
• Subjects incapable of multiple blood draws (HCT < 30mg/dL)
 
• Subjects with a history of rhabdomyolysis
 
• Subjects with a history of drug-related myalgias
 
• Subjects with a history or diagnosis of hemorrhagic tendencies or blood dyscrasias
 
• Subjects with a history of GI bleed or peptic ulcer disease
 
• Subjects who smoke tobacco or have ongoing alcohol or illegal drug use
 
• Subjects who are pregnant, lactating, or trying to conceive during the study period
 
• Subjects allergic to fluvastatin or rifampin or any known component of the medications
 
• Anyone who in the opinion of the study investigators is unable to do the study
 

TEST PRODUCT, DOSE, AND ROUTE OF ADMINISTRATION	Fluvastatin 20 mg by mouth as a 20 mg Lescol® capsule
	Rifampin 600mg IV infusion over 30 minutes (t = -30 minutes)
	Rifadin 600mg by mouth as two 300mg rifadin capsules
CONTROL PRODUCT, DOSE AND ROUTE OF ADMINISTRATION	Fluvastatin 20 mg by mouth as a 20 mg Lescol® capsule

DURATION OF SUBJECT PARTICIPATION AND DURATION OF STUDY	The time required for this study will include approximately: 5 minutes each day taking the rifampin capsule for 6 days, one 2-hour screening visit, and two 13 hour stays in the CRC (separated by at least 1 day). The total time required is 27 ½ hours over about a 8 day period. Additional time maybe required if study is prolonged for any reasons.

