## 4. STUDY DESIGN

### 4.1 Study Overview

The effect of rifampin on the pharmacokinetics of fluvastatin under a hepatic enzyme induced state will be studied in healthy volunteers in a two-period, randomized, unblinded, crossover clinical trial. For the first 5 days of the trial, the patients will be pretreated with 600mg oral rifampin (two 300mg rifadin capsule) once daily to induce hepatic enzymes (and transporters). For study period 1, subjects will be randomized to one of two treatment groups:

- (i) one oral dose of fluvastatin (Lescol®) 20mg capsule
- (ii) one oral dose of fluvastatin (Lescol®) 20mg capsule immediately following a 30-min intravenous infusion of rifampin 600mg in 10ml Normal Saline

The two study periods will ideally be on a Tuesday and Thursday, separated by one day of fluvastatin washout. The oral food intake will be standardized and subjects will be instructed to fast overnight the day before study period 1 and period 2, and for 3h post-dosing. In both treatments, venous blood samples (8ml each) will be drawn at 0, 0.33, 0.67, 1, 1.5, 2, 2.5, 3, 4, 6, 9, 12h after fluvastatin dosing. During the 1 day of fluvastatin washout, patients will continue pretreatment with one 600mg dose of oral rifampin. Period 2 will begin after 1 day of fluvastatin wash out, when subjects will receive the second treatment, followed by blood draws at the same time points after fluvastatin dosing. If study period two does not follow one day after study period one, it will most likely be conducted on Tuesday or

Thursday of the following week. In this case, the subjects would be maintained in a state of induction of hepatic enzymes by the same preinduction regimen with 600 mg of oral rifampin for 5 days before study period 2.

	Period 1	Period 2
Group 1	A	B
Group 2	B	A

A= fluvastatin; B =rifampin +fluvastatin

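### Does the single-dose protocol leave room for only 24 hours between IV rifampin and the control dose that follows it?

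*Combined protocol and SAP*

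**What the plan says.** The file holds two protocols. In the single-dose study, IV rifampin is given once, before fluvastatin, in one of the two periods. In the induction study, oral rifampin is taken daily for 5 days before Period 1 and again on the day between periods. The point concerns the single-dose study.

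Its section 4.1 states: "The two study periods will preferentially be on a Tuesday and Thursday, separated by one day of washout". Later in the same paragraph it sets a floor: "Period 2 will begin after at least a 1-day washout when subjects will receive the second treatment". Neither sentence names a drug, gives a half-life or says from when the day is counted. Section 10.2 is headed for Tuesday and section 10.3 for Thursday. The synopsis entry on duration says "subject will be on study for up to 2 days" and "The total time required is 27 hours over about 2 day period". It builds this from one 2-hour screening visit and 13-hour stays that are at least one day apart.

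The induction protocol, section 4.1, describes the same weekly pattern: "The two study periods will ideally be on a Tuesday and Thursday, separated by one day of fluvastatin washout". Its synopsis says: "The total time required is 27 ½ hours over about a 8 day period".

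Section 9.3 of the single-dose protocol adds: "Plasma concentrations of fluvastatin and rifampin in all collected plasma samples will be measured". That includes the time-0 sample of each period.

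**The concern.** Group 2 takes rifampin plus fluvastatin in Period 1 and fluvastatin alone in Period 2. Half of the control data therefore come after an IV dose of the inhibitor, and the washout has to clear rifampin as well as fluvastatin. The section does not say that it does. The sister protocol labels the same gap a fluvastatin washout, which could suggest that rifampin was not considered.

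The synopsis adds doubt. Tuesday to Thursday is three calendar days, not two, and two days could be taken to mean consecutive days with 24 hours between doses. The weekdays are only a preference, and the floor is not given in hours.

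The stake is the primary comparison. If residual inhibition raised the Group 2 control AUC, the pooled ratio would be pulled down. For a true ratio above 1 that means toward no effect, which is the result the sponsor expects (section 1.2).

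**Working it through.** **1. The synopsis figures.** Hours: 2 + 13 + 13 = 28, against 27 stated. The induction synopsis has the same one-hour shortfall: 2 + 26 + 6 × 5/60 = 28.5, against 27½ stated. The error is in the addition of participant time and has no bearing on the gap.

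Days: the induction protocol's 8 days are 5 pretreatment + Period 1 + washout day + Period 2. On that count the single-dose study takes 1 + 1 + 1 = 3 days, so its two-day figure does not reproduce. Two other ordinary counts do give 2: the two dosing days alone, or 48 hours from dose to dose. First dose to last sample is 48 + 12 = 60 hours, or 2.5 days.

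**2. Can the gap be 24 hours?** Consecutive-day dosing leaves 24 − 13 = 11 hours between stays. The synopsis requires at least one day, so it excludes the reading it was thought to allow. Taken literally, its shortest dose-to-dose gap is 13 + 24 = 37 hours (12 + 24 = 36 if counted from the last sample). Section 4.1 also requires an overnight fast before each period, which implies morning dosing. The first morning that satisfies 36–37 hours is the one 48 hours after the first dose.

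Section 4.1 itself ties one day of washout to Tuesday/Thursday, then uses the same term for the floor. The preference wording leaves the weekdays free, and the floor allows a longer gap. Neither shortens it.

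**3. Which drug?** The single-dose study gives only fluvastatin and rifampin, so an unqualified washout covers whatever Period 1 delivered. The induction study keeps oral rifampin going on the washout day, so it has to restrict the term to fluvastatin. The two wordings fit two designs and do not conflict.

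**4. Residual drug.** The half-life is assumed, since the documents give none. With simple exponential decline from the end of infusion (t = 0), the residual is 0.5^(gap ÷ half-life):

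| Gap | half-life 2 h | 5 h | 8 h |
|---|---|---|---|
| 24 h (excluded above) | 0.024% | 3.59% | 12.5% |
| 37 h (literal synopsis floor) | <0.001% | 0.59% | 4.05% |
| 48 h (Tuesday/Thursday) | <0.001% | 0.13% | 1.56% |

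**5. Effect on the estimate.** With equal sequences, the pooled log ratio is the mean of the two sequence log ratios. If carryover multiplied only the Group 2 control AUC by c, the pooled ratio would be multiplied by c^−0.5. For an assumed c = 1.1 this is 0.953, and for c = 0.9 it is 1.054. The documents give no basis for either value. They only show how a carryover effect would be diluted. Section 15.6 sizes the trial for a 50% difference.

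**The case for a change.** The best case for a change is that the adequacy of the washout is the assumption on which the Group 2 control rests, and the protocol never argues it. Two sentences and a short listing would cost almost nothing. The minimum has no stated start point. Section 4.1 of the induction protocol also speaks of Period 2 following one day after Period 1, which read literally is Wednesday. A shortfall in washout that raised the control AUC would favour the expected answer.

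Part of this stands. No rationale is given, and a reader would like one. The synopsis duration is loosely worded. Residual concentration is also not the whole of carryover, because an effect could outlast the drug.

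The rest carries less weight. The literal Wednesday reading comes from a different protocol, in a section that itself describes the pattern as Tuesday and Thursday. The documents do not show carryover. They tie induction to repeated daily oral dosing, and the glyburide results cited in section 1.2 of the induction protocol treat rifampin without pretreatment as the non-induced condition. The worrying residuals (3.59% and 12.5%) belong to a schedule the text rules out. The rifampin assay already covers the Group 2 Period 2 time-0 samples (six values with 12 subjects, five with 10), so analysts can check for residual drug without any new instruction. Section 15 also promises a detailed SAP before the final analysis. A listing would not change the primary result and could not exclude an effect that outlasts the drug.

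**Conclusion.** The concern does not call for a change. The planned interval has one sensible reading, about 48 hours from dose to dose, supported by section 4.1, the headings of 10.2 and 10.3, and the synopsis requirement on the separation of stays. At that interval, residual rifampin is at most about 1.6% of its end-of-infusion level under the longest assumed half-life of 8 hours. What remains is a missing sentence of rationale, which a reader can supply from the design, and a clerical slip in the synopsis (27 hours for 28, and two days for what another count makes three). Neither alters dosing, sampling, the estimate or its test.

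This rests on the assumed half-life range of 2–8 hours, on simple exponential decline, and on judging carryover by residual drug. The documents give no evidence of an effect that outlasts it.
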